To determine the diagnostic performance of index tests (audible handheld Doppler, visual handheld Doppler, ABPI, exercise ABPI and TBPI) for the diagnosis of PAD in patients with diabetes as determined by a reference test (CTA or MRA).

Secondary:

- To determine the cost-effectiveness of tests
- To determine the performance of tests using exploratory diagnostic thresholds
- To explore the effect of combining different tests on diagnostic performance
- To evaluate patient acceptability of tests
- To evaluate the effect of confounding patient characteristics (e.g., neuropathy and ulceration) on diagnostic performance
- To evaluate the performance of tests for establishing the severity of PAD
- To evaluate inter- and intra-rater reliability of tests
- To evaluate the performance of PAD-scan (in selected centres).

DESIGN

Prospective multicentre diagnostic accuracy study

SAMPLE SIZE

A total of 600 participants

INCLUSION/EXCLUSION CRITERIA

Inclusion criteria:

- Aged ≥ 18 years
- Known history of diabetes

Exclusion criteria:

- PAD status known on imaging
- Known history of PAD intervention
- CTA and MRA contraindications- renal impairment, pregnancy, contrast medium hypersensitivity/allergy, non-compatible implants (MRA only).
- Unable to provide appropriate informed consent.
- Interim surgical interventions (occurring in the time interval between index and reference tests) will be considered a protocol violation and patients will be excluded.

MAIN STUDY PROCEDURES (including intervention duration and follow-up)

VISIT 0

- Remote screening

VISIT 1 (will occur at a routine/planned visit):

- Eligibility check
- Recording of demographic detail and medical history
- Assessment for neuropathy
- Assessment of diabetic foot ulcer severity, if relevant
- Quality of Life questionnaire: the validated EuroQoL (EQ-5D-5L) questionnaire will be used to assess the generic QoL and will allow economic assessment
- Index tests for the diagnosis of peripheral arterial disease:
 1. Audible handheld Doppler
 - 2a. Visual handheld Doppler
 - 2b. PAD-scan (only in 3 selected centres)
 3. ABPI
 4. TBPI
 5. Exercise ABPI i.e., ABPI performed following repetitive heel raising.
- Patient acceptability; patients will be asked to rate their experience of each test on a Likert scale
- Blood test to assess renal function*
- Repeating of index tests by the same and by an alternative operator for the assessment intra- and inter-rater reliability, respectively (only performed in the first 100 volunteering patients)

*In some centres, the blood test to assess renal function may require a separate visit.

VISIT 2 (Within 6 weeks of visit 1)

- Reference scan (MRI or CTA)

OUTCOME MEASURES

Primary outcome

- Sensitivity of index tests

Secondary outcome(s)

- Specificity, likelihood ratios, predictive values and diagnostic odds ratio
- Health economic outcomes: 1) Cost of the test, including direct costs and amortisation of capital equipment and use of other healthcare resources for prevention and treatment of the disease over a time horizon of 5 years 2) Quality Adjusted Life Years at 5 years. 3) Incremental cost-effectiveness ratio at 5 years
- Patient acceptability
- Technical success
- Inter- and intra-rater reliability

1. BACKGROUND

Diabetes is a major global healthcare issue with an estimated prevalence of 9.3% (1). Over 6% of people with diabetes develop a diabetic foot ulcer (DFU) (2). DFUs are slow to heal (3), have a negative impact upon patients quality-of-life (4) and are associated with a 5-year lower limb amputation and mortality rate of 20% and 40% respectively (5). In addition, DFUs cost the NHS an estimated £1 billion per year (6).

Peripheral arterial disease (PAD) is a key risk factor in the development of DFUs (7) and is also associated with delayed DFU healing, increased risk of leg amputation and mortality (3,8). The detection of PAD in people with diabetes is fundamental though challenging. Although a variety of bedside tests are available, there is no agreement as to which is the most useful.

Review of existing evidence

Existing reviews (9,10) highlight the lack of evidence in this area. An updated systematic review and meta-analysis (11) has been performed to further evaluate the evidence for the numerous bedside tests in this cohort of patients.

MEDLINE and EMBASE databases were systematically searched for studies providing data on diagnostic performance of bedside tests used for the detection of PAD in people with diabetes. A meta-analysis was performed to obtain pooled estimates of sensitivity and specificity for the diagnosis of PAD. Eighteen studies, reporting on a total of 3016 limbs of patients with diabetes, were included in our qualitative review. Of these, 11 studies (1543 limbs) were included in the meta-analysis of diagnostic accuracy: **ABPI** (9 studies, 1368 limbs, sensitivity 63.5% [95% CI 51.7-73.9%], specificity 89.3% [CI 81.1-94.2%]); **TBPI** (3 studies, 221 limbs, sensitivity 83.0% [CI 59.1-94.3%], specificity 66.3% [CI 41.3-84.6%]); and **visual waveform assessment** (4 studies, 397 limbs, sensitivity 82.8% [CI 73.3-89.4%], specificity 86.8% [CI 75.5-93.3%]). Overall, there was a high risk of bias across studies, most frequently relating to patient selection and lack of blinding.

TEsting for Arterial disease in Diabetes (TrEAD) study

The largest study to date has been completed comparing the diagnostic performance of tests for the presence of PAD in patients with diabetes (Clinicaltrials.gov: NCT04058626; (12,13)).

This study enrolled 305 participants, across 2 centres. The performance of index tests (ABPI, TBPI, TcPO₂, pulse palpation, audible waveform (handheld Doppler) and visual waveform (handheld Doppler)) were compared to a blinded reference duplex ultrasound scan (DUS).

Alongside these commonly used bedside tests we have also evaluated the performance of an 'enhanced' visual waveform test that has been termed Podiatry Ankle Duplex scan (PAD-scan). PAD-scan is a new focussed DUS test that directly visualises the ankle vessels and detects more detailed waveforms. The results of the TrEAD study were consistent with the findings of our meta-analysis which suggested that visual waveform assessment may be the most promising modality. It was found that visual waveform assessment with **PAD-scan** had better sensitivity than **visual handheld Doppler** (95% vs 83%, p<0.001) justifying further evaluation, in a limited number of selected centres, in this proposed study. Sensitivities of other tests were: **audible Doppler** (74%), **TBPI** (60%) and **ABPI** (60%). **Pulse palpation** and **TcPO₂** had low sensitivities of 43% and 31% respectively, justifying exclusion from this

proposed study. Combining ABPI and pulse palpation with audible Doppler (sensitivity 84%, specificity 46%) or visual Doppler (sensitivity 87%, specificity 44%) improved sensitivity when compared to each test used in isolation. However, their combined performance was still inferior to the PAD-scan.

Cost-effectiveness of bedside tests

The cost-effectiveness of the bedside tests evaluated in the TrEAD study (14) has been estimated. A Markov model was constructed to estimate the health outcomes and costs over 5 years of different testing strategies applied to a cohort of patients with diabetes presenting to a hospital diabetic foot clinic where the prevalence of PAD and DFU was 66% and 40%, respectively. Health outcomes were incidence of new DFU, major cardiovascular events, lower limb amputation, death and DFU healing rates. Costs included those of the index tests plus further interventions as recommended by clinical guidelines.

It was found that **visual handheld Doppler** was the most cost-effective test. However, when including **PAD-scan** as part of the analysis then this dominated other options with an ICER of £11 391 per QALY. Its use would result in a reduction of the number of amputations by 24% and cardiovascular deaths by 10% over 5 years, as compared to TBPI (the next best alternative). PAD-scan had the highest probability (78.7%) of having the greatest net benefit at a willingness to pay threshold of £20 000 per QALY. PAD-scans superiority in ICER occurred at a PAD prevalence threshold of 24%.

Limitations of existing evidence

There are a number of important limitations relating to currently available evidence, which we aim to address in this proposed study.

- **Patient selection-** No single study has represented the full spectrum of patients with diabetes seen in primary and secondary care.
- **Index and reference tests-** Index tests were performed by experts whose experience may not represent the general workforce. All studies have used DUS as the reference test, which may be less reliable in interrogating the commonly affected distal vessels in diabetes (15,16) as compared to CTA or MRA.
- **Analysis by limb-** Most studies evaluated diagnostic performance by performing bilateral scans and interpreting results in each limb independently. This is a potential source of bias as the presence of PAD in one limb increases the probability of PAD being present in the other.
- **Visual waveform assessment-** A significant arterial lesion results in morphological change in the waveform detected in the downstream circulation. Although visual waveform assessment has been shown to be a promising modality there is currently no agreed definition of an 'abnormal' waveform. Waveform morphology exists on a spectrum according to the severity of disease; triphasic (normal), biphasic, and monophasic (abnormal). For the diagnosis of PAD, some studies use a monophasic cut-off (17,18) whilst others use a biphasic waveform as the threshold for diagnosis (19). The TrEAD study showed that overall test accuracy can be improved by using an **enhanced definition** for defining abnormal waveforms (13). This involves identifying biphasic waveforms with adverse morphological features i.e., spectral broadening, infilling of the spectral window, long forward flow or slow systolic rise time. This enhanced definition improved sensitivity as compared to the traditional monophasic waveform

threshold (95% vs 77%), and improved specificity as compared to the biphasic waveform threshold (77% vs 21%). However, a potential limitation of the TrEAD study was that visual handheld Doppler assessment may have been disadvantaged by not using this enhanced definition, which was only evaluated for the PAD-scan. In this proposed study this enhanced definition, which has been shown to be superior, will be used as the primary diagnostic threshold for visual waveform assessment.

Why this research is needed now

This research is of significant priority given the rising global prevalence of PAD (20) and diabetes (21) which will increase the burden of diabetic foot disease and place further pressures on healthcare services. Missed diagnosis of PAD is common (22), and is an important cause of avoidable amputations (22–24). Our health economics modelling has demonstrated that improvements in the detection of PAD are not only cost-effective but also may considerably reduce the number of lower limb amputations and cardiovascular deaths by enabling clinicians to optimise treatment. This will help mitigate the expected rise in disease prevalence.

The TrEAD study (13), our meta-analysis (11) and cost-effectiveness study have identified visual waveform assessment as a putative front runner. We have also demonstrated that a new enhanced definition for waveform interpretation and a new enhanced visual waveform test (PAD-scan) may further improve diagnosis. These novel findings may deliver significant and meaningful impact but require further validation (13).

2. OBJECTIVES AND ENDPOINTS

2.1 Primary Objective

To determine the diagnostic performance of index tests (audible handheld Doppler, visual handheld Doppler, ABPI, exercise ABPI and TBPI) for the diagnosis of PAD in patients with diabetes as determined by a reference test (CTA or MRA).

2.2 Secondary Objective

- To determine the cost-effectiveness of tests over a time horizon of 5 years
- To determine the performance of tests using exploratory diagnostic thresholds
- To explore the effect of combining different tests on diagnostic performance
- To evaluate patient acceptability of tests
- To evaluate the effect of confounding patient characteristics (e.g., neuropathy and ulceration) on diagnostic performance
- To evaluate the performance of tests for establishing the severity of PAD
- To evaluate inter- and intra-rater reliability of tests
- To evaluate the performance of PAD-scan (in selected centres).

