2.4 Secondary Endpoints

- Specificity, likelihood ratios, predictive values and diagnostic odds ratio.
- Health economic outcomes: 1) Cost of the test, including direct costs and amortisation of capital equipment and use of other healthcare resources for prevention and treatment of the disease over a time horizon of 5 years 2) Quality Adjusted Life Years at 5 years. 3) Incremental cost-effectiveness ratio at 5 years
- Patient acceptability
- Technical success
- Inter- and intra-rater reliability: The first 100 volunteering patients will be consented to have index tests repeated by the same operator and by an alternative operator on the same leg.

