Full details of the methods and justification of the sample sizes will be included in the comprehensive Statistical Analysis Plan, authored by the study statistician and agreed by the independent TSC. The Statistical Analysis Plan will be prepared and finalised prior to database lock.

Index test diagnostic thresholds

The performance of the index tests based on prespecified diagnostic thresholds for PAD will be evaluated. These thresholds have been selected as they demonstrated optimal

diagnostic performance in the TrEAD study or are commonly used in clinical practice. However, other thresholds have been described in the literature and there is no consensus as to which are best. Therefore, different 'exploratory' thresholds will be evaluated as part of our secondary analyses. Tests generating continuous results (ABPI, TBPI and exercise ABPI) will be evaluated for performance based on optimised thresholds derived from Receiver Operating Characteristics (ROC) analysis. A 'net benefit' approach will be used (as a sensitivity type analysis over a range of plausible thresholds) following ideas for assessing the clinical utility of prognostic models summarised in Riley R et al (*Prognostic Research in Health Care; 2018; Oxford; section 7.4.3 page 168-170*). From this, it should be possible to integrate cost-effectiveness parameters into assessing the best threshold.

Diagnostic thresholds:

- o Visual waveform assessment- monophasic or biphasic waveforms with adverse features.
- o Audible waveform assessment- monophasic waveform
- o ABPI- ≤ 0.9 in either vessel
- o TBPI- < 0.75 in either vessel
- o Exercise ABPI (31)- Post exercise ABPI ≤ 0.9 in either vessel.

Health economics analysis

A literature review will be conducted to identify published health economic studies in similar patient groups. Cost-effectiveness of the tests will be estimated using Markov models that simulate clinical events in a cohort of hypothetical patients with diabetes over 5 years. The structure of the model may follow that developed in previous work by this group (reference 14). Depending on their PAD status (PAD or no PAD), and ulceration status at presentation (DFU or no DFU), patients will be allocated into one of eight initial states following a test: True positive (with and without DFU), true negative (with and without DFU), false positive (with and without DFU), or false negative (with and without DFU).

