True and false positive patients without DFU will be prescribed orthotics and additional foot checks, in addition to standard care. True and false positive patients with DFU will undergo confirmatory DUS, and, if confirmed positive, angiography, revascularisation and low dose rivaroxaban, in addition to standard care. True and false negative patients will continue with standard care for the remainder of the 5 year time horizon. The accuracy of test outcomes will be obtained from the study. The probability of clinical events (new DFU incidence and healing rates of DFU, amputation of unhealed limbs, cardiovascular events and death) and treatment effects associated with recommended interventions for diagnosed PAD patients (e.g., orthotics, revascularisation, rivaroxaban) will be obtained from NICE evidence reviews and the literature. The study will be conducted from the perspective of the UK NHS and Personal Social Services according to NICE methodological guidelines and reported according to CHEERS standards. Costs, QALYs, ICERs and measures of uncertainty over 5 years will be estimated. Test costs will be estimated by bottom-up costings during the course of the study that will include machine capital acquisition cost and one-off training (amortised over the useful life and expected through-put of patients per year), consumables and operator time. Prices and unit costs of items will be obtained from manufacturers and national databases.

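### The cost-effectiveness analysis stops at 5 years with no stated reason and no longer scenario, although the modelled benefits include averted amputations and deaths

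*Protocol*

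**What the plan says.** The horizon is the same wherever the protocol states one. The objective in section 2.2 is "To determine the cost-effectiveness of tests over a time horizon of 5 years". Section 2.4 lists "2) Quality Adjusted Life Years at 5 years. 3) Incremental cost-effectiveness ratio at 5 years", and the outcome list in the Trial Summary repeats this. Section 8.4 (Health economics analysis) plans "Markov models that simulate clinical events in a cohort of hypothetical patients with diabetes over 5 years" and closes with "Costs, QALYs, ICERs and measures of uncertainty over 5 years will be estimated".

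The events in the model are "new DFU incidence and healing rates of DFU, amputation of unhealed limbs, cardiovascular events and death". The Background describes foot ulcers as "associated with a 5-year lower limb amputation and mortality rate of 20% and 40% respectively". It reports the benefit found in the group's earlier model, whose structure may be reused, as a "reduction of the number of amputations by 24% and cardiovascular deaths by 10% over 5 years".

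Neither document gives a reason for 5 years, a longer scenario, an extrapolation, or any credit at year 5 for patients still alive. SAP section 3.3 places health economics outside the SAP.

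**The concern.** A model with a fixed end date gives no value to anything after it. That does little harm if the differences between strategies have played out by then. Here two of the modelled benefits, avoiding amputation and avoiding death, continue for the rest of the patient's life. On the protocol's own figure, 100% − 40% = 60% of patients with a foot ulcer are still alive when counting stops.

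What is at stake is a secondary objective: whether the comparison of tests on cost and QALYs holds beyond a window that the plan does not justify. The primary endpoint (sensitivity) and the sample size are not affected.

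**Working it through.** **Figure to reproduce.** There is none for this study. The Background gives £11 391 per QALY for PAD-scan in the earlier 5-year model. It cannot be rebuilt, because the documents give no incremental costs, incremental QALYs, utilities, transition probabilities or discount rate. What can be checked is how much survival benefit falls after the cut-off.

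**Input from the documents.** 5-year mortality with a foot ulcer: 40% (Background).

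**Assumptions not in the documents.** A person spared death then has the cohort's mortality. Averted deaths are timed like the deaths themselves. The hazard is constant, or rises by 5%, 9% or 12% a year. The discount rate is 0% or 3.5%.

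**Step 1, hazard.** h = −ln(1 − 0.40)/5 = 0.5108/5 = 0.102 per year.

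**Step 2, constant hazard, undiscounted.** A death averted at time t earns (1 − e^(−h(5−t)))/h by year 5 and 1/h over a lifetime. Averaged over deaths in years 0 to 5:

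- share after year 5 = 5h·e^(−5h)/(1 − e^(−5h)) = 0.5108 × 0.6/0.4 = 0.766
- lifetime = 1/h = 9.79 life-years
- by year 5 = (1 − 0.766) × 9.79 = 2.29 life-years

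**Step 3, discounted at 3.5%.** The same integrals give 2.05 against 6.74 life-years, so 1 − 2.05/6.74 = 70% falls after year 5.

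**Step 4, hazard rising with time.** Use h(t) = a·e^(gt) with a = −ln(0.6)·g/(e^(5g) − 1), so that 5-year mortality stays at 40%. Share falling after year 5, by numerical integration:

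| Hazard | Undiscounted | 3.5% |
|---|---|---|
| Constant | 77% | 70% |
| Rising 5% a year | 69% | 64% |
| Rising 9% a year | 65% | 60% |
| Rising 12% a year | 63% | 58% |

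Lifetime life-years are therefore about 1/(1 − 0.58) = 2.4 to 9.79/2.29 = 4.3 times those counted by year 5.

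**Step 5, other mortality levels (assumed).** With constant hazard, undiscounted and then at 3.5%: 20% mortality gives 89% and 81%; 60% gives 61% and 55%; 70% gives 52% and 46%. At 60% mortality with a rising hazard the range, over both discount rates, is about 44% to 54%. So the share can drop below half once 5-year mortality is about 60% to 70% or more.

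**Step 6, an effect that lasts only 5 years.** Suppose the mortality hazard is 10% lower for 5 years (0.0919) and then returns to 0.102. The figure is illustrative and is not the earlier model's 10% for cardiovascular deaths. Survival at year 5 is e^(−5 × 0.0919) = 0.6315 instead of 0.6.

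- Within 5 years: 0.3685/0.0919 − 0.4/0.1022 = 0.093, or 93 life-years per 1000 patients
- Afterwards: (0.6315 − 0.6)/0.1022 = 0.308, or 308 per 1000
- Share afterwards: 308/(93 + 308) = 77%

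The result does not need a treatment effect beyond year 5.

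**Step 7, from life-years to the ICER.** The lifetime ICER is (ΔC₅ + ΔC_later)/(ΔQ₅ + ΔQ_later). With positive increments it equals the 5-year ICER only if ΔC_later/ΔC₅ = ΔQ_later/ΔQ₅. The documents give none of these four quantities, so the calculation stops at life-years.

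**The case against.** A reader might infer that the 5-year ICERs are distorted against a threshold, that most of the QALY gain is lost, or that another test would be preferred over a longer horizon. The documents support none of these, for five reasons.

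- **Threshold.** This study sets none. The £20 000 per QALY in the Background belongs to the earlier analysis.
- **Costs.** Later costs are cut off as well. Section 8.4 attaches further foot checks and drug treatment to some test-positive patients without saying for how long. If these continue past year 5, a longer horizon adds costs along with QALYs. Nor does any figure show that cost differences between tests fall mainly at the start.
- **Ranking.** In the earlier 5-year model PAD-scan was already preferred, at £11 391 per QALY with a 78.7% probability of greatest net benefit. If a longer horizon added only QALYs for the more sensitive test, that choice would be strengthened.
- **QALYs.** The model also counts new ulcers, healing and amputation. Their quality-of-life effects fall partly within 5 years, so the life-year share is not the QALY share.
- **Population.** The 40% is for patients with a foot ulcer, whereas the study also recruits from primary care and the model has states without an ulcer.

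All five stand, and they limit the conclusion. It can also be said that scenario runs may sit in a separate economic plan, given that section 8.4 commits to NICE methods, CHEERS reporting and measures of uncertainty. That is possible, but the documents mention no such plan and no longer run. None of this supplies a reason for stopping at 5 years.

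**Conclusion.** The point holds as a cheap improvement to a secondary analysis. The 5-year cut-off is applied consistently and without justification to a model whose benefits include averted amputation and death.

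At the protocol's mortality for patients with a foot ulcer, more than half of the life-years from a death averted within 5 years fall after the cut-off in every variant tried: about 63% to 77% undiscounted and 58% to 70% at 3.5%. This rests on an assumed hazard shape, on average cohort mortality for those spared, and on a figure for ulcer patients only. It describes life-years from averted deaths. The direction and size of any change in an ICER, and whether the preferred test would change, remain unknown. That uncertainty is a reason to run the longer scenario; it is not evidence that the 5-year answer is wrong.

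**What to change.** In protocol sections 2.2, 2.4 and 8.4:

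1. Keep the 5-year results as the stated endpoint and give the reason for choosing 5 years.
2. Add a pre-specified lifetime-horizon scenario of the same Markov model, with costs and QALYs extended together.
3. State the extrapolation assumptions: event and death rates after year 5, how long treatment effects and treatment costs continue, utilities, and the discount rate.
4. Report both sets of ICERs side by side and say whether the preferred test changes.

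Because SAP section 3.3 leaves health economics out, the detail needs a place in the protocol or in a health economics analysis plan, fixed before the accuracy results are known.

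The cost is more cycles of the same model and the work of setting the extrapolation; no new data are collected. The downside is that late-year rates are uncertain and must be extrapolated. That uncertainty can be shown in the measures of uncertainty that section 8.4 already plans.
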